### *CHW Curriculum*

Participants enrolled in the CHW intervention will receive group-based health education sessions:

Curriculum Session Title & Content	Tailored cultural components
Session 1: Diabetes Overview 
 
• Diabetes information
 
• Prevention of diabetes
 
• Myths and Facts about diabetes
 
• Goal-setting
 
	
 
· Concept of prevention tied to South Asian core values (in religion/culture)
 
· Discussion of diabetes prevalence and increased risk of diabetes in Asians
 
· Discussion of diabetes among South Asians
 
· Explanation of BMI and at-risk BMI in Asian communities
 
· Dispelling common cultural misconceptions regarding diabetes (eg. getting diabetes is a natural part of aging)
 
· Incorporation of culturally appropriate images and language
 

Session 2: Healthy Eating 
 
• Nutrition and Food
 
• Eating a balanced diet: The Plate Method
 
• Overcoming barriers to eating out/social situations
 
• Reading a Nutrition Label
 
• Goal-setting for healthy eating
 
	
 
· Photos of typical South Asian foods
 
· Healthy elements in traditional South Asian cooking (eg. whole grain options for rotis, incorporating fruits and vegetables)
 
· Identifying and limiting deep-fried snacks high in salt and sweets high in fat and sugar; substituting sweets with fruits
 
· Healthy vegetarian options
 
· Healthy versions of popular South Asian recipes
 
· Following the Plate Method with traditional South Asian foods
 
· Managing expectations for eating out, langar at gurdwara (for Sikhs), etc.
 
· Reading food labels
 
· Working with women participants to improve nutrition in the entire household
 
· Incorporation of culturally appropriate images and language
 

Session 3: Physical activity 
 
• Caloric intake and energy
 
	
 
· Discussion of physical activity as essential to physical and mental fitness (eg. encouragement to practice similar discipline in physical activity as in prayer)
 


 
balance
 
• Benefits and types of exercise
 
• Injury prevention
 
• Incorporating routines
 
• Overcoming barriers
 
• Practice activity and goal-setting
 
	
 
• Home-based exercise/activities
 
• Practice Activity
 
• Incorporation of culturally appropriate images and language
 

Session 4: Diabetes Management and Complications
 
 
• Diabetes complications
 
• Heart disease and stroke
 
• Staying motivated and goal-setting
 
• Discussion of diabetes complications, heart disease, stroke
 
• Discussion of prevention and inter-connectedness of chronic diseases
 
• Discussion of cholesterol and fats in diet, blood pressure and salt in diet
 
	
Review of popular South Asian foods high in salt and fat and limiting these foods
 
 
• Incorporation of culturally appropriate images/language
 

Session 5: Stress and family support
 
 
• Effects of stress on health
 
• Stress and anger management
 
• Strategies to manage depression
 
 
Family support and goal-setting
	
 
• Discussion of meditation practice
 
• Progressive muscle relaxation for stress relief
 
• Strategies to manage depression; discussion around stigma associated with mental health (eg. depression)
 
• Incorporation of culturally appropriate images and language
 

## A2. Data Collection

### *EHR Data*

Data will be extracted from the PCPs' EHR systems by an NYU staff member every 6 months. De-identified EHR data will be collected from both intervention and control participants. The process for collecting de-identified patient data is described here: This will entail NYU study staff exporting de-identified patient information via a secure sftp site to a central repository managed by NYU. In order to de-identify patient information, unique study identifiers will be assigned to patients by associating a specific study number with a specific medical record number in the EHR system. The table of study identifiers and corresponding medical record numbers will be kept at each PCP for the duration of the study in a secure and locked location in their respective clinics. All other potentially identifying data will also be stripped from the dataset prior to extraction. Only the PCPs will retain the table necessary to link patient identifiers and the study ID. Using this method, we will ensure that patient confidentiality is maintained, but that patients who are observed more than once will have the same study ID in each extraction, which is necessary for the planned analyses. Using the described approach, a pre-defined set of patient data will be exported every 6 months from the clinics' EHR systems into a de-identified Excel spreadsheet or delimited text file. Data elements will be based on functionalities of EHR platforms and will include patient demographic information such as year of birth, gender, race/ethnicity, diagnoses, medications, laboratory dates, and Alc readings.

Follow-up height and weight measures will be obtained during routine office visit at six months. Scheduled office visits will be tracked via quarterly data pulls from the PCPs. If no visit is scheduled during the follow-up period, project CHWs will conduct follow-up calls to schedule patients for a height and weight recording at the clinic. Patient travel incentives will be provided to facilitate follow-up data collection.

Extracted de-identified data on patients include the following::

- i. De-identified EHR data will include the following:
  - Practice site ID and demographics - gender, age, race/ethnicity (if available), Language (if available)
  - Any diagnoses for: hypertension, diabetes, pre-diabetes, and high cholesterol during the study period , including month and year of diagnosis
  - Height and weight data during the data collection period, Month and year of measurement
  - All lab results for: A1c, lipid profile during the study period, Month and year of measurement
  - All BP measurements (systolic and diastolic) during the study period, Month and year of measurement
  - Dates of clinic visits

De-identified claims data obtained from the Healthfirst data warehouse to be provided to the study team includes:

- All hospital admissions and ED visits during the intervention period (Study ID, Bill type, Encounter type, Admission Month/Year, Length of stay, DRG, Primary ICD 9/10 diagnosis code, Secondary diagnosis codes, if available, ICD 9/10 procedure codes, Attending physician specialty, Allowed Amount, Discharge status, Admit type, Admit source)
- Pharmacy claims (Study ID, Drug generic names, Drug class, Dates of Fill (month/year only), Total Drug Cost Amount)
- Outpatient claims (Study ID, Primary ICD 9/10 diagnosis code, Secondary diagnosis codes (up to 5), if available, ICD 9/10 procedure codes, Allowed Amount, Month/year of claim, Physician specialty)
- Lab claims (Study ID, Allowed amount, Month/year of claim, Type of test)

## B. Data Analysis and Data Monitoring

### B1. Aim 1 Analysis

AIM 1: To compare the effect of the EHR/CHW intervention with usual care on weight loss. The primary outcome will be probability of eligible patients at a PCP to lose 5% or more of their body weight six months following the index office visit.

Secondary outcomes include: Average reduction in HbA1c, % sustained >5% weight loss at 12 months; improved lipids and blood pressure 6- and 12- months following the index office visit.

*Hypothesis:* Individuals receiving care during the implementation of the EHR/CHW intervention will be more likely to lose 5% of their body weight six months following the index office visit than individuals receiving care as usual. This will translate directly to a commensurate increase in the proportion of the study sample under the EHR/CHW intervention losing 5% of their body weight relative to the care as usual group.

The analysis of the effect of EHR/CHW on the outcome measure will be based on a Generalized Linear Mixed Model (GLMM). In particular, we will use a random effects model that assumes a binomial

distribution with a logit link function. The comparison will make no linear assumption about the time trend for each outcome over the course of the trial. The model will be as follows:

$$(1) \quad \text{logit}(Y_{ijt}) = \mu + \alpha_j + \theta_t + \tau C_i,$$

where  $Y_{ijt} = 1$  if the  $i^{\text{th}}$  subject attached to the  $j^{\text{th}}$  site at time quarter  $t$  loses 5% or more her body weight six months following the index visit,  $Y_{ijt} = 0$  otherwise.  $\alpha_j$  is a random effect for site  $j$  with mean 0 and variance  $\sigma_b^2$ .  $\theta_t$  is a time-specific effect a quarter  $t$ ,  $t \in (1, 2, \dots, 12)$ .  $C_i$  is an indicator variable, and  $C_i = 1$  if individual  $i$  receives care under the EHR/CHW intervention,  $C_i = 0$  if individual  $i$ .  $\tau$  represents the treatment effect of the intervention. The model will be fit using the LME4 package using R software. The hypothesis will be tested using two-sided level of significance  $\alpha = .05$ . Because outcome data will be derived from administrative data, we do not anticipate missing data. However, in the event that there is missing data, we will use multiple imputation under the assumption of data missing at random (MAR). This is consistent with following intent-to-treat protocol.

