## C. Study Design

### C1. Overall Design/Site Selection/Site Enrollment

We will use a randomized controlled trial design with staggered-entry and a waitlist controlled group to compare the effectiveness of an alert and registry-driven CHW-led coaching compared with usual care among patients with BMI at baseline of  $\geq 23 \text{ kg/m}^2$ . Randomization will be at the individual-level and stratified by PCP, meaning eligible intervention and control participants will be randomized for each PCP. PCPs will be clustered into waves, aligning with the original stepped-wedge design. Entry into the study will be staggered in three waves, with each wave consisting of six to seven PCPs (See Figure 1). All 20 PCPs will be recruited and enrolled by month 6 of Year 2 (study period 6, Figure 1), and we will assign 6-7 practices into each of the 3 waves upon enrollment. For each PCP, there will be a total of two rounds of consecutive six-month CHW intervention periods: 1 month for recruitment and enrollment of intervention participants and five months of community health worker-led group education sessions (approximately one session per month). Data related to the study outcomes will be extracted from EHR systems a total three times (baseline, 6 month, and 12 month) for each PCP. Randomization at each PCP will occur during the first round. Prior to allocation into treatment group, each treatment participant will be matched to a control participant based on age, gender, and BMI. Intervention participants will be split into two groups and assigned to either first or second round. All control participants will be waitlisted during the first round and will be offered the full CHW group education sessions during the second round. PCPs will be placed into waves based on geographic location and CHW caseload considerations. PCPs will be eligible for participation if they have a) an overall patient volume of  $N \geq 1000$ ; b) at least 70% of the patient population is South Asian; and c) the practice has used EHR for at least 12 months. All PCPs will sign a Memorandum of Understanding (MOU) between the PCP and NYU outlining study commitments.

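### Aim 1 credits the treatment effect to EHR/CHW against usual care, but both arms have the practice-wide EHR tools, so the trial estimates assignment to the CHW package given those tools

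*Combined protocol and SAP*

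**What the plan says.** Section III.B1 sets the objective as "AIM 1: To compare the effect of the EHR/CHW intervention with usual care on weight loss". Its hypothesis is that "Individuals receiving care during the implementation of the EHR/CHW intervention will be more likely to lose 5% of their body weight" at six months than people under care as usual, and it expects a "commensurate increase in the proportion of the study sample under the EHR/CHW intervention". In model (1), C_i is 1 if the patient "receives care under the EHR/CHW intervention"; the definition of C_i = 0 breaks off before it says anything. Section I.C1 describes the trial as one to "compare the effectiveness of an alert and registry-driven CHW-led coaching compared with usual care".

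On design, I.C1 says "Randomization will be at the individual-level and stratified by PCP", and also "Prior to allocation into treatment group, each treatment participant will be matched to a control participant based on age, gender, and BMI". Section I.C2 has the EHR changes made at each PCP. III.A1 lists the alert and the registry among the minimum components for all participating practices. The CHW Protocol in I.C2, and again VI.A, draw eligible patients from registry lists and then randomize them.

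**The concern.** The protocol describes its intervention as two components, an EHR alert with registry and CHW-led coaching. A comparison can credit the pair against usual care only if some arm or period has neither. If every randomized patient attends a practice that already has the first component, a positive result would be reported as evidence for the integrated model when the data speak only to the CHW part.

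This matters beyond labelling. The protocol directs its findings to payers. III.B2 (Cost-Effectiveness/Sustainability) asks what the integrated intervention cost and what different combinations of CHW and EHR interventions yielded. A mislabelled effect would sit in the denominator of the incremental cost per person achieving 5% weight loss.

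Two lesser matters concern model (1). It omits the variables used for matching. It also has one site intercept shared by both arms, although the intervention is taught in groups.

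**Working it through.** **1. What differs by arm**

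| Element | Intervention | Control | Source |
|---|---|---|---|
| EHR alert and HbA1c prompt | yes | yes | I.C2, III.A1 |
| Registry | source of patients | source of patients | I.C2 CHW Protocol, VI.A |
| Coaching and referral materials open to providers in the EHR | yes | apparently yes | III.A1 |
| Group sessions and up to 9 calls | yes | waitlisted | I.C1, I.C2 |
| CHW templates and progress notes fed back to the provider | yes | no CHW contact while waiting | III.A1 |

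Randomization is within PCP and follows the registry draw, so the first three rows cancel in tau. The last two remain. The wording about care received during implementation suits the stepped-wedge layout, which I.C1 refers to as the original design.

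**2. Cost questions.** Two arms give one contrast: the CHW package given the EHR tools. Different combinations of CHW and EHR cannot be compared. EHR costs either cancel between arms or, if charged to the intervention arm, are set against an effect that excludes them. Moreover, VI.G (Control Participants) says no claims data are collected from controls, while III.B2 compares resource use between arms.

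**3. Timing of teaching.** I.C1 assigns part of the intervention arm to the second round and offers controls the sessions during that same round. The section on waitlisted controls has them contacted after Round 1. The CHW Protocol and VI.A say after completion of the intervention rounds. Depending on the index date, some intervention patients may be untaught, or some controls taught, when the six-month weight is recorded.

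**4. The plan's own power figure.** 520 per arm x 0.85 = 442 analysed. No control rate is given. A two-sided 0.05 test for an 8-point difference has power 93.0%, 85.9% and 79.6% at assumed control rates of 10%, 15% and 20%. The stated figure of above 80% holds up to a control rate of about 19.6%. It is compatible with the plan, with no allowance for group correlation.

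**5. Group correlation (illustrative).** 26 x 0.85 is about 22 per PCP in the intervention arm, or about 11 in each of two groups. With correlation in one arm only:

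- design effect DE = 1 + (m - 1) x ICC
- ratio of true to reported standard error r = sqrt((1 + DE)/2)
- actual type I error = 2(1 - Phi(1.96/r))

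| Assumed ICC | m = 11: DE, r | Type I error | m = 6: type I error |
|---|---|---|---|
| 0.01 | 1.10, 1.025 | 5.6% | 5.3% |
| 0.02 | 1.20, 1.049 | 6.2% | 5.6% |
| 0.05 | 1.50, 1.118 | 8.0% | 6.5% |

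In a simulation of model (1) with half attendance, no matching effect and an assumed 12% event rate, the error was 5.3%, 5.2% and 5.6% at the three ICCs.

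**6. Covariates.** In the same kind of simulation at an assumed 12% against 20%, adding the matching variables moved the average tau from 0.62 to 0.65 when their combined logit SD was 0.5, and to 0.71 when it was 1.0, with the risk difference fixed at 8 points. The odds-ratio scale shifts with adjustment; the marginal risk difference does not.

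**The case against.** The best defence is that the I.C1 sentence has coaching as its noun, so it may be read as coaching against no coaching, with alert and registry as background. That is a fair reading of that one sentence, and it makes the remedy largely editorial. It does not rescue Aim 1 or the hypothesis, which name EHR/CHW. Nor can the alert and registry count as usual care: section B3 says the lower BMI threshold has not been formally adopted in clinical settings, and Contributions presents the alert and registry as an innovation of the project.

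A reader might infer that tau isolates coaching and contains nothing electronic. The documents do not support that. III.A1 puts CHW templates and progress reports into the EHR, and this feedback follows CHW contact, so it belongs to the package that tau estimates.

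A reader might also infer that group teaching makes the primary test invalid. That is not shown. Every ICC here is assumed. Several sessions run weekly, so classes may not be fixed, part of the coaching is by individual calls, and attendance may be partial because invitation follows randomization. All of these reduce the inflation. The premise that controls are untaught before six months is itself unsettled (working, item 3).

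**Conclusion.** The contrast in Aim 1, the hypothesis, tau and the I.C1 design sentence is wrong as written. This rests on the text and needs no numerical assumption. The trial can estimate assignment to the CHW package added to practice-wide EHR tools, against those tools with a waitlist. Assignment is the right word only if every randomized patient is analysed as randomized, and the plan mentions intent-to-treat only in its missing-data sentence.

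This does not mean that the EHR tools are ineffective, or that the randomized comparison is biased by the label. The EHR effect is simply not identified.

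Adjusting for the matching variables is a low-cost improvement, not the repair of an error. The clustering point is conditional: about 5.6% to 8.0% type I error under assumed ICCs of 0.01 to 0.05 with 11 per group and full attendance, and less otherwise. It supports a sensitivity analysis and no more.

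**What to change.** (a) Restate Aim 1, the hypothesis, tau and the I.C1 sentence as assignment to the CHW package (group sessions, calls, CHW-provider feedback) added to the practice-wide EHR tools, versus the same tools with waitlist. Define C_i = 1 and C_i = 0 as the randomized arms, with all randomized patients analysed as assigned. Reconcile I.C1, the I.C2 CHW Protocol, the waitlisted-control section and VI.A on when second-round intervention patients and controls receive sessions relative to the six-month outcome. In III.B2, say that the incremental cost is for the CHW package given the EHR tools, drop the question on different combinations, and reconcile the arm comparison with the absence of control claims data in VI.G.

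(b) Add age, gender and baseline BMI to model (1) and report the marginal risk difference. All three can be had from data already extracted.

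(c) Pre-specify, as a sensitivity analysis, a risk-difference regression of the six-month outcome on randomized arm with PCP, quarter and these covariates, using a small-sample-corrected cluster-robust standard error by PCP (20 clusters, t with 19 df).

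The cost is text edits and one further model. The analysis in (c) loses power. Simulated at an assumed 12% against 20%, it had 78% to 91% over ICCs of 0 to 0.05, against 88% to 92% for model (1); part of the gap at the higher ICC reflects model (1)'s inflated error. It should therefore not replace the primary test.

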### **CHW Component:**

CHW Protocol. Patients that meet eligibility criteria will be drawn from registry lists and randomized to intervention or waitlisted control. Patients assigned to the intervention group will be sent an invitation letter to participate in the CHW intervention (See *Recruitment Letter for CHW Intervention*). Invitation letters will be followed up with phone calls by CHWs (See *Script for Telephone Screening for CHW Intervention*). In addition, a screening form (See *Telephone Screening Form for CHW Intervention*) will be completed to verify eligibility. CHWs will call patients a maximum of 10 times over a two-week period at varying times of day to invite them to enroll into the study. Patients assigned to the waitlisted control group will be recruited and contacted in the same manner as intervention participants except after completion of intervention rounds.

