### *Consenting and data collection with Intervention participants*

Consent forms will be completed with intervention participants in an in-person meeting. Baseline surveys will also be conducted by NYU study staff with intervention participants within two weeks after consent. (See *CHW Participant Baseline Survey*). A CHW Participant Followup Survey will be completed with intervention participants approximately six months after the start of intervention in order to evaluate the effectiveness of the CHW intervention.

Participants enrolled during the COVID-19 pandemic will be asked questions on vaccine hesitancy and COVID19 vaccination; as well as questions on mental health and mobile/technology use in order to understand how participants' chronic conditions and mental health was affected in during the pandemic and to understand how best to tailor remote intervention strategies to encourage vaccination among patients with overweight and pre-diabetes who are at higher risk for complications from COVID-19.

The CHW intervention includes a protocol that consists of 5 monthly 90-minute group health education sessions, providing the tools and strategies to prevent diabetes. All sessions employ adult learning techniques and group-based learning and activities. All session materials have been culturally and linguistically adapted into Bengali, Urdu, Hindi, Punjabi, and Nepali. Sessions will be held in remotely via audio phone calls via telephone, MCIT NYU approved Webex and Zoom platform or in community spaces identified by partner agencies, and multiple sessions will be held weekly to accommodate patient's varying schedules. Links to the health education sessions will be created via NYU approved Webex and Zoom platforms that are provided for use across the institution. These NYU Webex and Zoom links will be shared to participants via text message through NYU MCIT secured phones(see Text Message Script). The study team has developed training materials on how to use the NYU Webex and Zoom platforms to provide to research participants. Use of the Zoom will be used solely for the purpose of delivering the health education materials and will not involve discussion of PHI. In order to maintain anonymity for Zoom, for each session, the study staff will create Zoom waiting rooms for participants to be renamed as "Participant 1, Participant 2, etc.) prior to individuals joining the larger session with other research participants.

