#### Consenting and data collection with waitlisted control participants

For control participants, the study will collect EHR data on clinical measures only that will be linked to a unique identifier housed at the primary care practices; there will be no survey data collection with control participants. In other words, the study will not be evaluating changes in study outcomes via non-EHR data among waitlisted control participants who receive the CHW intervention. For these reasons, we are requesting a waiver of authorization (see *Section IVb Process of Consent*). After completion of Round 1 intervention with intervention participants, CHWs will call contact waitlisted control participants regarding the group education sessions. Control participants will be offered the same content and dosage of education sessions.

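### Model (1) omits the matching variables and cannot absorb correlation from group teaching in one arm; the net effect on the error rate is not established, and both should be handled in one prespecified change

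*Combined protocol and SAP*

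**What the plan says.** **Design (section C1).** Randomisation is individual and stratified by PCP. Before allocation, "each treatment participant will be matched to a control participant based on age, gender, and BMI". Each PCP runs two consecutive six-month rounds: "Intervention participants will be split into two groups and assigned to either first or second round".

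**Order of events (CHW Component; section VI.A).** Eligible patients "will be drawn from registry lists and randomized to intervention or waitlisted control". Invitation, telephone screening and consent come afterwards.

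**Delivery (Consenting and data collection with Intervention participants).** The programme is "5 monthly 90-minute group health education sessions", with several sessions offered each week, plus CHW telephone calls.

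**Primary model (section III.B1).** It is a logistic mixed model with an intercept, quarter effects, a treatment indicator C_i and α_j, which "is a random effect for site". There is no age, gender, BMI or pair term, and no CHW, session-group or site-by-treatment term. C_i is defined by the care a person receives; the same section says that the handling of missing data follows intent-to-treat.

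**Timing for controls.** Section C1 says that controls "will be offered the full CHW group education sessions during the second round". The waitlist consent section says that CHWs contact them "After completion of Round 1 intervention with intervention participants". The CHW Protocol says that they are recruited as intervention patients are, "except after completion of intervention rounds"; section VI.A agrees with the CHW Protocol.

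**Power.** An 8-point difference is to be detected with more than 80% power, with 1040 randomised 1:1, 15% loss and 20 PCPs. Neither a control rate nor an ICC is stated.

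**The concern.** Two features of the design are missing from the model, and they act in opposite directions.

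- **Matching.** Matched partners should have positively correlated outcomes. An analysis that ignores this overstates the standard error, so the test is conservative and precision is lost.
- **Group teaching.** If patients taught together do better or worse together, their outcomes are correlated in the intervention arm only. A site intercept shared by both arms largely cancels from the within-site contrast and does not pick this up, so the standard error is understated.

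The actual error rate of the primary test therefore depends on which omission dominates, and the plan gives no means of knowing.

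Two definitions add to this. Because randomisation precedes invitation, a literal reading of C_i could code a patient randomised to intervention who never enrols as a control. And because the passages on control timing differ, the index visit and quarter t of a control are not defined.

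**Working it through.** **1. The plan's own figure.** Evaluable per arm: 520 × 0.85 = 442. Power = Φ(0.08/SE − 1.96), with SE² = [p(1−p) + (p+0.08)(0.92−p)]/442. The control rate p is not given, so it is varied. At p = 0.20, SE² = (0.1600 + 0.2016)/442, so SE = 0.0286 and power is 79.9%. Power is 93.2%, 86.2% and 74.9% at p = 0.10, 0.15 and 0.25. The claim of more than 80% therefore holds up to a control rate of about 20% (19.9%) without clustering. It is not shown to be wrong.

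**2. Inputs for the error rate.**
- Cluster size: 26 × 0.85 ≈ 22 per arm per PCP. An equal split over two rounds (assumed) gives 11. Taking 11 as a session group, or 22 as one CHW's patients, is also an assumption.
- ICC 0.01 to 0.05 and pair correlation ρ = 0.05 or 0.10: assumed.
- Uptake u: 100%, or 41%. The 41% is the screening-to-enrolment rate that the Sampling paragraph reports from another study. That it carries over as uptake among those randomised is an assumption.

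**3. Formulas.** With m followed up per group, the intervention-arm design effect is DE = 1 + (m−1)·ICC. With uptake u, let a = u·m; then DE = 1 + a(a−1)·ICC/m. True variance over model variance under the null is r = (1+DE)/2 − ρ, and actual alpha = 2[1 − Φ(1.96/√r)].

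**4. Each omission alone.**
- Matching ignored, no clustering: r = 0.95 gives 4.4%; r = 0.90 gives 3.9%.
- Clustering ignored, no matching, full uptake, ICC 0.01/0.02/0.05: 5.6/6.2/8.0% (m = 11) and 6.2/7.5/11.3% (m = 22).

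**5. Both omissions, model (1) as written, ρ = 0.05.** Alpha in %:

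| Case | ICC 0.01 | ICC 0.02 | ICC 0.05 |
|---|---|---|---|
| 41% uptake, m = 11 | 4.5 | 4.6 | 4.8 |
| 41% uptake, m = 22 | 4.6 | 4.8 | 5.4 |
| Full uptake, m = 11 | 5.0 | 5.6 | 7.4 |
| Full uptake, m = 22 | 5.6 | 6.9 | 10.7 |

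Example, full uptake, m = 11, ICC 0.05: DE = 1.50, r = 1.25 − 0.05 = 1.20, alpha 7.4%. Example, 41% uptake, m = 22, ICC 0.05: a = 9.02, DE = 1 + 9.02 × 8.02 × 0.05/22 = 1.164, r = 1.032, alpha 5.4%.

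**6. Covariates added, standard error otherwise unchanged.** The ratio becomes r/(1−ρ). At ICC 0 it is 0.95/0.95 = 1, so alpha moves from 4.4% to the nominal 5.0%. At full uptake, m = 11, ICC 0.05, it is 1.20/0.95 = 1.263, so alpha moves from 7.4% to 8.1%.

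**7. Simulation check** (20 PCPs, 22 per arm per PCP, control rate 15%, pair correlation about 0.05, full uptake, 2,400 trials per case). Model (1) as written gave 4.5% at ICC 0. At ICC 0.02/0.05 it gave 6.0/7.8% (groups of 11) and 7.7/11.8% (one CHW for 22). Adding the covariates alone gave 5.2%, 6.8/8.9% and 8.4/12.5%. The pattern matches the closed form, with somewhat higher values. Monte Carlo SE is about 0.45 points near 5%, and √(0.118 × 0.882/2400) = 0.66 points at 11.8%.

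**8. Power with clustering.** Multiplying the intervention-arm variance by DE = 1.20 (groups of 11, full uptake, ICC 0.02) lowers the highest control rate that gives 80% power from 19.9% to about 16.6%.

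**The case against.** The strongest reply is that the excess error may not exist. Randomisation precedes invitation, so patients who never attend dilute any group effect. At 41% uptake the combined rate is 4.5-5.4%. The Sampling paragraph also assumes that 30% will consent to CHW contact and an HbA1c test; used as uptake, that gives 4.5-4.9%. Several sessions are held each week, so groups may be smaller than 11: at an assumed 5 per group, full uptake and ICC 0.02, r = 1.04 − 0.05 = 0.99 and alpha is 4.9%. If the programme changes nobody's weight, there is no group correlation from it and no excess error. Leaving out matching covariates does not invalidate a randomised comparison. All of this stands.

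Four stronger readings are tempting, and the documents do not support them:
- A reader might infer that the primary test has an inflated error rate. That needs values of ICC, group size and uptake that are not given.
- A reader might infer that adjusting for covariates alone makes matters worse. It raises the error rate above nominal only if arm-only clustering is appreciable; with none, it brings the test to its nominal level.
- A reader might infer that only the intervention arm is taught in groups throughout the six-month comparison. That holds for round 1; for round 2 it depends on passages that conflict.
- A reader might infer that one remedy is required, such as a PCP-level jackknife. Random-effect alternatives exist, and in simulation with one CHW serving two PCPs, leaving out PCPs gave 7.0/9.4% at ICC 0.02/0.05.

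It can also be said that C_i is loose wording, since the plan mentions intent-to-treat and even randomisation. That is probably the intention, but the definition should say so.

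**Conclusion.** Both omissions are real on the text. Ignoring the matching costs precision and makes the test conservative (alpha 4.4% or 3.9% at assumed pair correlations of 0.05 or 0.10, no clustering). The site intercept cannot absorb correlation confined to one arm. The net error is not established: over the assumed ranges it runs from slightly below nominal to about 10.7% in closed form, and the upper values need full uptake, an ICC of 0.05 and one CHW's 22 patients acting as a cluster. The case for change is that the error rate should not depend on unknown quantities when the remedy is cheap. The definition of C_i and the control timing need correcting whatever the ICC. This is a change that should be made; confidence in its practical size is moderate.

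**What to change.** 1. Define C_i as the randomised arm.
2. Add age, gender and baseline BMI to model (1) as fixed covariates.
3. Together with item 2, prespecify a standard error for the treatment effect that allows for arm-specific correlation within PCP. Options are a site-by-treatment random effect, a CHW or group random effect in the intervention arm only, or PCP-level jackknife or cluster-robust inference with a small-sample correction. The choice is the sponsor's.
4. Record CHW and session group for each intervention participant. If either crosses PCPs, use it as the clustering unit.
5. State the control rate and ICC behind the power claim, and restate power.
6. Reconcile section C1, the CHW Protocol, the waitlist consent section and section VI.A on when controls are offered sessions, and define the index visit and quarter t for controls.

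**Cost.** Items 1 to 3 are mainly SAP wording: site ID, age, gender, height and weight are already in the EHR extract. A CHW or group random effect would also need the identifiers in item 4, which are not in that extract. The price is a slightly wider interval. For the jackknife version, simulated power at 15% against 23% without clustering is 84%, compared with 87% for model (1). With 19 degrees of freedom and no gain from covariates, 80% power then holds for control rates up to about 16.6% instead of 19.9%.
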